# Number of Subjects:

As a pilot study, in a new cohort of participants, using a wait-list control, we are not able to calculate an accurate sample size. In order to evaluate feasibility and effect size, and allowing for up to 20% drop outs, we will arbitrarily enroll up to 24 subjects to achieve a goal of having 20 subjects complete the study per protocol (estimated 10 per group).

## Number of HCC/CCC Sessions and Length of Study:

All baseline measures, along with a brainwave assessment, will be obtained during an enrollment visit (V1). The intervention will commence 0-14 days later. Participants will receive 8-16 in-office intervention sessions over a maximum of 4 weeks. HCC sessions will be about 1.5-2 hours in length. Participants may receive two intervention sessions during a half day period. All will receive a total of 6 sessions during the first three days of the intervention period. Participants will be encouraged to complete the remainder of the intervention sessions within two-three weeks, with a maximum of four weeks to complete the sessions. If received as two sessions per half day, subject involvement will thus require 4-8 half days during the intervention period. Following the initial 6 sessions, some sessions may be arranged as singles (one per day), if needed due to schedule issues.

In the HCC group, one to fourteen days after the final intervention session there will be a postintervention data collection visit (V2). V2 will be 4-6 weeks after V1 for the CCC group. All measures will be repeated at V2, but no brainwave assessment will be obtained. An intermediate post-intervention data collection visit, will occur at four to six weeks after completion of the intervention for the HCC group, and 8-10 weeks after V1 for the CCC group, with all measures repeated. Data collected at the V3 visit will comprise the primary outcome data for the study. A final data collection visit (V4) will occur 12-14 weeks after completion of the intervention for the HCC group, and 16-18 weeks after V1 for the CCC group, with repeat of the outcome measures and a brainwave assessment. At V4, official study involvement is complete for those in the HCC group, while those randomized to the CCC group will be offered an opportunity to be scheduled to receive a course of HCC. Those who accept will receive a course of in-office acoustic stimulation linked to brainwaves (brainwave assessment 0-14 days before starting sessions), as described for the HCC group, and will continue to be followed for data collections at 1-14 days (V5), 4-6 weeks (V6), and 12-14 weeks (V7), as done during the initial intervention period, after completing their HCC sessions. Participants will have up to 3 months to crossover.

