Measures will be collected at an enrollment visit (V1), for both groups. Intervention will begin 0-14 days thereafter for the HCC group. BP and heart rate (HR) recording will be repeated prior to the start of the 7th session for the HCC group. Post-intervention data collections will include an immediate postintervention visit (V2, 1-14 days after intervention completion for HCC, 4-6 weeks after V1 visit for CCC), an intermediate post-intervention visit (V3, primary outcome, 4-6 weeks after intervention completion for HCC, and 8-10 weeks after V1 for CCC), and a final follow up visit (V4, 12-14 weeks following completion of the intervention for HCC, and 16-18 weeks after V1 for CCC). The primary outcome will be differential change in the systolic and diastolic BP from V1 to V3. Following V4, those in the CCC group will be offered an opportunity to receive a course of HCC. Those who accept will have a brainwave assessment 0-14 days before starting sessions and continue to be followed for data collections at 1-7 days (V5), 4-6 weeks (V6), and 12-14 weeks (V7) after completing their HIRREM sessions. Participants will have up to 3 months to crossover. We will utilize linear mixed models (LMMs) to contrast longitudinal changes in systolic and diastolic blood pressure between the HCC and CCC groups. Mean contrasts will be used to compare the changes in blood pressures between groups from V1 to V3, our primary test of efficacy. Additional mean contrasts will be constructed to evaluate the consistency of any benefit of HIRREM through subsequent visits beyond V3. Comparisons of changes in all secondary outcomes will be assessed in a similar fashion.

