Those who have no other exclusions, are interested to participate, and provide informed consent will be randomly assigned to receive 8-16 sessions of in-office acoustic stimulation linked to brainwave activity (HCC), over a maximum of 4 weeks, while continuing their other current clinical care, or to continue their current clinical care alone (CCC). There will be pre- and post-intervention data collection to include systolic and diastolic BP, and many secondary outcome measures including measures of autonomic cardiovascular regulation (continuous recording of BP and HR for calculation of measure of HRV and BRS), behavioral symptom outcomes (ISI, PSQI, ESS, CES-D, GAD-7, PCL-C, PSS), quality of life measure (Quality of Life Scale, QOLS), short physical activity recall (International Physical Activity Questionnaire, IPAQ-SF), and function performance measures (drop stick reaction testing, and grip strength). All measures will be collected at an enrollment visit (V1), for both groups. Intervention will begin 0-14 days thereafter for the HCC group. BP and heart rate (HR) recording will be repeated prior to the start of the 7th session for the HCC group. Post-intervention data collections will include an immediate postintervention visit (V2, 1-14 days after intervention completion for HCC, 4-6 weeks after V1 visit for CCC), an intermediate post-intervention visit (V3, primary outcome, 4-6 weeks after intervention completion for HCC, and 8-10 weeks after V1 for CCC), and a final follow up visit (V4, 12-14 weeks following completion of the intervention for HCC, and 16-18 weeks after V1 for CCC). The primary outcome will be differential change in the systolic and diastolic BP from V1 to V3. Following V4, those in the CCC group will be offered the opportunity to receive a course of HCC, and those who accept will have up to 3 months to schedule a brainwave assessment 0-14 days before starting sessions and continue to be followed for data collections at 1-14 days (V5), 4-6 weeks (V6), and 12-14 weeks (V7) after completing their HIRREM sessions.

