# Post-Intervention Data Collection Visits:

For participants in the HCC group, between 1-14 days after completion of the intervention, participants will return for a post-intervention data collection visit (V2). Those in the CCC group will return at 4-6 weeks after V1. All measures will be repeated, but no brainwave assessment done. This visit will take about 45 minutes.

Between 4-6 weeks after completion of the intervention, participants in the HCC group will return for the primary outcome data collection visit (V3). This will occur at 8-10 weeks after V1 for those in the CCC group. All measures will be repeated, including a brainwave assessment. This visit will require about 120 minutes.

Between 12-14 weeks after completion of the intervention, participants in the HCC group will return for a final data collection visit (V4). The V4 visit will be between 16-18 weeks after V1 for those in the CCC group. All measures including a brainwave assessment will be repeated for a final time. This will complete the official study involvement for participants in the HCC group, while those in the CCC group will be offered an opportunity to be scheduled to receive a course of HCC, and this will be discussed. This visit will take about 120 minutes.

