## Other Data Collection, Measures, and Process:

A series of measures will be collected at the enrollment visit (V1), as well as at three post-intervention period visits for all participants. Those in the CCC group, who later receive HCC, will also have an additional three post-interventions data collection visits.

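### No blood pressure is scheduled between V4 and the first HIRREM session for control participants who cross over, so the V5-V7 changes can rest on a value about 3 months old

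*Combined protocol and SAP*

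**What the plan says.** **Time allowed for crossover.** The section Number of HCC/CCC Sessions and Length of Study says "Participants will have up to 3 months to crossover", and the Abstract says the same. The Overview words it differently: "those who accept will have up to 3 months to schedule a brainwave assessment 0-14 days before starting sessions".

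**What happens before the crossover course.** Number of HCC/CCC Sessions names one procedure, "brainwave assessment 0-14 days before starting sessions), as described for the HCC group". The Abstract and Overview also name only this assessment. None of the three mentions BP at that appointment.

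**What happens after it.** Other Data Collection, Measures, and Process says that these participants "will also have an additional three post-interventions data collection visits". Number of HCC/CCC Sessions gives the timing: they "will continue to be followed for data collections at 1-14 days (V5), 4-6 weeks (V6), and 12-14 weeks (V7") after the course ends. The Abstract has a different first window: "data collections at 1-7 days (V5").

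**The last BP before the course.** This is V4, which falls 16-18 weeks after V1 in the CCC group. Post-Intervention Data Collection Visits says of V4: "All measures including a brainwave assessment will be repeated for a final time".

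**The comparison arm.** In the HCC group all baseline measures are taken at V1, and "The intervention will commence 0-14 days later".

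**Baseline for V5-V7.** Neither the Abstract nor Statistical Analysis names one.

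**The concern.** HCC participants start sessions with a BP at most two weeks old. Crossover participants start the same course with a BP that may be about three months old, although they are already due to be seen shortly before session 1.

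A before-after change at V5, V6 or V7 then has two parts: whatever happened to BP between V4 and the first session, and whatever happened from the first session on. Only the second can reflect HIRREM. The HCC group's involvement ends at V4, so no concurrent group is scheduled from which the first part could be estimated. A change in lifestyle or season, a drug start, or ordinary variation in those weeks would be counted as before-after change.

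The omission cannot be repaired later: once crossover sessions begin, a pre-course value cannot be recovered. What is at stake is how far three extra visits per crossover participant can be interpreted. The randomised comparison is not at stake.

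**Working it through.** The plan states no figure for the age of the crossover baseline, so there is none to reproduce. The check is interval arithmetic on its visit windows.

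**Inputs**
- Crossover allowance: up to 3 months, taken as 13 weeks × 7 = 91 days (Abstract; Number of HCC/CCC Sessions).
- Overview wording: 3 months to the assessment, then up to 14 days to the first session, so 91 + 14 = 105 days.
- HCC arm: V1 to first session, at most 14 days.
- Course length: at most 4 weeks = 28 days.
- Upper visit windows after the course: V2 and V5, 14 days; V3 and V6, 6 weeks = 42 days; V4 (HCC) and V7, 14 weeks = 98 days.

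**Step 1: age of the latest pre-course BP at the first session**
- HCC: 0-14 days.
- Crossover: 0 to about 91 days, or 0 to about 105 days on the Overview wording.

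**Step 2: longest interval from that BP to each visit**

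Maximum interval = age at first session + course length + upper visit window.

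| Visit (HCC / crossover) | HCC, from V1 | Crossover, from V4 | Crossover, Overview wording |
|---|---|---|---|
| V2 / V5 | 14 + 28 + 14 = 56 | 91 + 28 + 14 = 133 | 105 + 28 + 14 = 147 |
| V3 / V6 | 14 + 28 + 42 = 84 | 91 + 28 + 42 = 161 | 105 + 28 + 42 = 175 |
| V4 / V7 | 14 + 28 + 98 = 140 | 91 + 28 + 98 = 217 | 105 + 28 + 98 = 231 |

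The excess is the same at every visit: 91 − 14 = 77 days, or 105 − 14 = 91 days. On the Abstract's V5 window the first crossover maximum would be 91 + 28 + 7 = 126 days, which does not alter the picture.

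**Step 3: where the gap enters**

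Change from V4 to a later visit = (BP at first session − BP at V4) + (BP at that visit − BP at first session). The first bracket enters in full, and nothing scheduled measures it.

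**Step 4: could another scheduled reading serve?**
- V1 is older than V4. It was also the eligibility check, with BP required to fall in range, which invites regression to the mean.
- The recording before the seventh session (Intervention Period) may carry over to crossovers, but it comes after six sessions and is not a baseline.

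**Step 5: with BP taken at the pre-session assessment**

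The age at first session becomes 0-14 days. The maxima become 56, 84 and 140 days, equal to those of the HCC arm.

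**The case against.** **The text may be incomplete rather than wrong.** The study flow chart has a part for the CCC participants who choose HIRREM, and it is not legible in the copy reviewed. A BP box could be there. The course is also said to run as for the HCC group, whose assessment takes place at V1 alongside all baseline measures. Against that, Other Data Collection counts only three added visits, all after the course. What stands is that the text schedules no such BP; the flow chart should be checked.

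**Three months is a maximum.** Someone who starts within 14 days of V4 has a BP as recent as any HCC baseline. V4's own brainwave assessment might then suffice, leaving no separate appointment. This stands, and the fix allows for it.

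**Nothing stated depends on V5-V7.** The primary test is the randomised V1-to-V3 contrast and the secondary objectives are comparisons with CCC. The planned contrasts beyond V3 may mean V4 only, and uptake of the offer is unknown. This stands and limits the importance of the point.

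**Stronger readings that the documents do not support.** A reader might infer any of the following:
- *Crossovers have no BP before HIRREM.* They have V1 to V4. What is missing is a new reading after V4.
- *The gap produces a bias of a given size in mmHg.* The documents give no rate of BP drift. The pilot BP changes come from supine continuous recording in other cohorts, so they are no yardstick for seated oscillometric BP here.
- *Crossover courses would greatly enlarge the data behind the pilot's effect-size estimate, or are meant to be pooled with HCC.* No section says so. Nor would a recent baseline make the two changes equivalent: V1 was an eligibility gate for HCC, a crossover reading would not be one, and the period from first session to V7 would remain uncontrolled.

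**Conclusion.** The point holds as a limited weakness in an uncontrolled extension. In the protocol's text, the latest pre-course BP for a crossover participant can be about 91 days old at the first session (about 105 on the Overview wording), against at most 14 days in the HCC arm. Baseline-to-visit intervals can be 77 to 91 days longer than their HCC counterparts. Any BP change in the gap goes into the V5-V7 changes, and no concurrent control is scheduled to reveal it. Its size in mmHg cannot be stated from the documents.

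This rests on four things: 3 months read as 91 days; participants using the full allowance; V4 serving as the V5-V7 baseline, an inference since none is named, though every other pre-course value is older; and the flow chart containing no additional BP. The primary contrast and the enrolment number are unaffected. This is an inexpensive improvement rather than a condition for running the trial.

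The conflicting V5 windows are a separate drafting inconsistency and neither support nor weaken this conclusion.

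**What to change.** 1. At the brainwave assessment already required 0-14 days before crossover sessions, take BP by the method in the Blood Pressure (BP) section: three seated readings, the last two averaged.
2. Name that value in Statistical Analysis as the baseline for changes at V5, V6 and V7. Where V4 itself falls within 14 days of the first session, let V4 serve.
3. State that the crossover change will be reported as an uncontrolled, descriptive before-after estimate, separate from the randomised comparison.
4. Put the reading in the schedule and flow chart, and settle whether the 3 months run to the assessment (Overview) or to the crossover itself (Abstract; Number of HCC/CCC Sessions).
5. Separately, reconcile the V5 window, which is 1-7 days in the Abstract and 1-14 days in the Overview and Number of HCC/CCC Sessions.

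The cost is a few extra minutes per crossover participant and a short text change. No new visit or change in sample size is needed. The fix shortens the unmeasured gap but does not supply a control group for the crossover period.

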## Enrollment Visit:

Informed consent is obtained, and blood pressure is then obtained. All participants will have been previously documented to have prior blood pressure values that meet the parameters for the lower risk sub-group of Stage 1 primary hypertension. In light of variability associated with visits to the doctor, or other factors, if blood pressure values are too high, or too low on the initial measurements the potential participant will be allowed to rest for at least 3 minutes, and the blood pressure will be repeated. Those who still have blood pressure values less than 130 mmHg systolic pressure, and diastolic pressure less than 80 mmHg, and thus do not meet criteria for Stage 1 hypertension, will be considered as screen failures. Those with blood pressure that is still higher than 140 mmHg systolic or 90 mmHg diastolic, will be also be considered as screen failures. They will not be assigned a study number, and will be excluded from further participation. Those with blood pressure values that are too high will also be advised to follow up with their medical provider. For those who meet blood pressure goals, notification of group assignment is made, and all baseline measures are collected, including a brainwave assessment. If not already completed via a REDCap link, a brief medical history form will be completed (Appendix C). Prior to randomization, women of childbearing potential will also have a urine pregnancy

test performed at the WFBH Outpatient Laboratory, 2nd floor, Piedmont Plaza 1 Building. If positive, they will be excluded from the study. The V1 visit will require about 2 hours of time.

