Importance: This study will explore the use of HIRREM for the newly defined lower risk sub-category of Stage 1 primary hypertension, a condition now lacking evidence-based therapies in a randomized, clinical trial. The primary outcome, change in blood pressure, is a practical, objective physiological parameter. The objective secondary outcomes evaluating autonomic cardiovascular regulation, may also provide important insights about the importance of the autonomic nervous system, as well as the impact of stress, in this setting. The study will confirm feasibility of a randomized clinical trial using a closed-loop acoustic stimulation intervention in this population, identify any unique challenges for working with this cohort, and provide estimates of effect size, which might justify larger controlled trials. A positive result would suggest that HIRREM may have benefit as a noninvasive, non-drug alternative for initial management of Stage 1 hypertension. The study will also help to identify characteristics of subgroups that might experience differential effects/benefits from HIRREM, and will allow evaluation of any impact on autonomic cardiovascular regulation.

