Interested subjects will be informed with a more detailed description of the study, and the extent of their commitment, through phone calls or email communications. If no exclusions are apparent from initial phone or email communications, potential participants will complete an online eligibility screening form, which will be reviewed by the study team. If potential participants express continued interest in the project and have no major exclusions, and after receipt of BP and cholesterol testing documentation as noted above, the cardiovascular risk will be calculated. If confirmed that they have < 10 % risk for cardiovascular disease, they will be scheduled for an enrollment visit (V1) at which time an informed consent will be completed. As part of the informed consent process, study procedures, schedule for visits, and duration of participation will again be reviewed, and alternatives discussed, including the option to not enroll in this project, and follow up with their primary health care provider.

After informed consent is obtained, a blood pressure will be obtained to confirm eligibility. Those with BP less than 130 mmHg systolic or 80 mmHg diastolic, or systolic BP  $\geq$  140 mmHg systolic, or  $\geq$  90 mmHg diastolic, will be considered as screening failures, and will not move on to the remaining enrollment visit activities. For those confirmed to have an eligible baseline blood pressure reading, a brief medical history will be obtained, randomization will be completed, and baseline study measures obtained, prior to the start of the intervention, or continuation of current care. Those scheduled for an enrollment visit will also be provided a copy of Appendix B, Handout to Study Participants, and/or a welcome email with details. Prior to randomization, women of childbearing potential will also have a urine pregnancy test performed at the WFBH Outpatient Laboratory, 2nd floor, Piedmont Plaza 1 Building. If positive, they will be excluded from the study.

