# Blood Pressure (BP):

For evaluation of blood pressure (BP) values that will be used to qualify for participation in the study, and for analysis of the primary outcomes, BP measurements will be obtained using an automated oscillometric blood pressure device. BP will be obtained in the left arm, with the participant sitting comfortably, and the left arm resting on a desk/table. Three samples will be obtained and the last two averaged to get the value that will be used as the reading for that visit (Kaplan NM, & Rose BD, 2010).

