## **Functional Measures:**

## **Reaction Testing:**

Reaction testing will be evaluated by a drop-stick, clinical reaction time apparatus. It is constructed from a meter stick covered in friction tape with gradations. The modified meter stick is fixed to a weighted rubber cylinder. The apparatus is placed between the thumb and index finger of the subject

and released at a random time during a countdown. The subject catches the apparatus and the distance fallen (cm) is converted to reaction. Following two practice trials, subjects perform eight trials, and a mean distance value is used for analysis. This is repeated with a second set of 8 trials later during the enrollment visit, and the mean distance value from the second trial will be used as the baseline value. Use of the average distance from the second set of trials will be used as the baseline value so as to avoid the impact of learning effect for this test. Only one set of trials will be used for comparison at follow up data collections. This simple clinical measure has been evaluated by Eckner et al., and demonstrated utility in testing comparable to computerized testing methods (Eckner JT, Kutcher JS, & Richardson JK, 2010). Our pilot data demonstrate improved reaction testing associated with use of HIRREM for athletes with persisting post-concussion symptoms (Tegeler CH, et al., 2016).

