## Statistical Analysis:

Continuous variables will be summarized with standard descriptive statistics, such as quartiles, means, and standard deviations, while categorical variables will be summarized with percentages and frequencies. LMMs will be employed to contrast longitudinal changes in systolic and diastolic blood pressure between the HCC and NCC groups. Mean contrasts will be used to compare the changes in blood pressure between groups from V1 to V3, our primary test of efficacy. Comparisons of changes in all secondary outcomes will be assessed in a similar fashion. Assumption and computation diagnostics will be assessed for all model fits (Cheng J, et al., 2010), and model adjustments and outcome variable transformations will be made as necessary. Data will be analyzed using SAS v9.4 (SAS Institute, Inc., Cary, NC) or the R Statistical Computing Environment.

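### Participants are told their group before the secondary-outcome baselines are collected at V1, in a wait-list trial with no masking described

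*Combined protocol and SAP*

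**What the plan says.** The Enrollment Visit section opens with "Informed consent is obtained, and blood pressure is then obtained". For those whose reading qualifies, it continues: "notification of group assignment is made, and all baseline measures are collected, including a brainwave assessment". The Participants/Subjects section gives a compatible order. After an eligible reading and a brief medical history, "randomization will be completed, and baseline study measures obtained, prior to the start of the intervention, or continuation of current care". It does not mention when participants are told their group.

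Three other places bear on this:

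- **Reaction Testing.** The baseline comes from a "second set of 8 trials later during the enrollment visit, and the mean distance value from the second trial will be used", which places it well into the visit.
- **Statistical Analysis.** Blood pressure is analysed by contrasts of change between V1 and V3 from linear mixed models. Then: "Comparisons of changes in all secondary outcomes will be assessed in a similar fashion".
- **Blood Pressure (BP).** One seated oscillometric procedure supplies the "values that will be used to qualify for participation in the study, and for analysis of the primary outcomes".

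The Number of Subjects section calls the control a wait-list. No masking of participants or assessors is described for this trial.

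**The concern.** A participant who has just learned that HIRREM sessions are about to start, or that they will not be offered until after V4 at 16 to 18 weeks, then rates their sleep, mood, anxiety, stress and quality of life and performs effort-dependent tests. That knowledge can move the answers. The risk is most plausible for the self-report scales, grip strength and reaction time. It is less direct for the PSQI (one-month recall), the ESS (usual chances of dozing), the IPAQ-SF (last 7 days) and the resting autonomic recording.

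The bias could run either way. Disappointed controls who score worse at V1, or hopeful HIRREM participants who score better, would make HIRREM look less effective. HIRREM participants who overstate their symptoms at V1 would make it look more effective.

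The Importance paragraph of the Abstract says the pilot is meant to "provide estimates of effect size, which might justify larger controlled trials". Effect sizes for the secondary outcomes are part of what a larger trial would be built on, so a distorted baseline bears on a stated purpose.

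**Working it through.** **Order of events.** The two V1 descriptions compare as follows.

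| Section | Order as listed |
|---|---|
| Enrollment Visit | consent, qualifying BP, notification of group, all baseline measures; medical history form and pre-randomization pregnancy test mentioned afterwards |
| Participants/Subjects | consent, qualifying BP, medical history, randomization, baseline measures; pre-randomization pregnancy test mentioned afterwards |

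Neither paragraph is strictly chronological, since the pregnancy test must come before randomization but is mentioned last. Even so, both list assignment ahead of the baseline battery, and no section reverses this. The qualifying BP comes before notification in both.

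**Size, by illustration.** The plan has no figure of its own on this point. The only input taken from it is 10 completers per arm (Number of Subjects). Everything else is assumed: equal SDs at both visits, no true effect, a two-sided 5% test, and

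- s = shift between arms at V1, in SD units
- k = fraction of that shift still present at follow-up
- r = pre/post correlation, 0.5 to 0.7

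With complete data the contrast is a difference in mean change. Its error is s(1 − k) SD. Its standard error is √(2(1 − r)) × √(2/10) SD, which is 0.447 for r = 0.5 and 0.346 for r = 0.7. The noncentrality is their ratio, on 18 degrees of freedom. For s = 0.25 and k = 0 it is 0.25/0.447 = 0.559 or 0.25/0.346 = 0.722.

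| Shift s | k | Error in estimate (SD) | False positives, r = 0.5 | r = 0.7 |
|---|---|---|---|---|
| 0.10 | 0 | 0.10 | 5.5% | 5.9% |
| 0.25 | 0 | 0.25 | 8.3% | 10.5% |
| 0.25 | 0.5 | 0.125 | 5.8% | 6.4% |
| 0.50 | 0 | 0.50 | 18.5% | 27.7% |
| 0.50 | 0.5 | 0.25 | 8.3% | 10.5% |
| any | 1 | 0 | 5.0% | 5.0% |

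Under disappointment or hope, with s = 0.25, k = 0 and r = 0.5, the 8.3% splits into 7.6% falsely favouring control and 0.6% falsely favouring HIRREM, against 2.5% each with no shift.

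**With baseline adjustment.** The plan does not name this analysis, but it would shrink a transient shift. The error becomes r × s, the standard error √(1 − r²) × √(2/10), with 17 degrees of freedom. For k = 0 this gives 6.1% and 8.1% (s = 0.25; r = 0.5 and 0.7), and 9.4% and 17.9% (s = 0.5). Simulation that includes the extra variance from baseline imbalance gives 6.0%, 7.9%, 9.0% and 16.4%.

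**With the protocol's own pilot SDs.** Table 2 under Specific Relevant Pilot Data gives baseline and change SDs from 10 participants. For s = 0.25 and k = 0, the spurious difference is 0.25 × baseline SD and the standard error is change SD × √(2/10).

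| Scale | Baseline SD | Change SD | Spurious difference | SE | False positives |
|---|---|---|---|---|---|
| ISI | 7.2 | 4.6 | 1.8 points | 2.06 | 13.2% |
| GAD-7 | 3.8 | 4.3 | 0.95 points | 1.92 | about 7.5% |
| CES-D | 11.7 | 9.8 | 2.9 points | 4.38 | 9.7% |

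**The case against.** The strongest reply has four parts.

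1. **The order is inferred.** The Enrollment Visit text joins notification and measurement with a plain conjunction and is not chronological elsewhere, so the site may in practice measure first. That is possible. But a protocol should not leave it open, and both descriptions point the same way.
2. **The harm is hypothetical.** Its size and sign are assumed. A 0.1 SD shift barely matters, and the 18.5% to 27.7% figures need a half-SD shift that disappears completely, so they should be read as an extreme case. The pilot SDs are far from equal between visits and imply correlations of about 0.89 (ISI), 0.09 (GAD-7) and 0.62 (CES-D), so the 0.5 to 0.7 range is only a convenience. This is right about the illustration, but it does not remove the exposure.
3. **False-positive rates are a weak yardstick.** The plan states no significance level, and its aim for these outcomes is estimation. That is fair; the more relevant measure is the error in the effect estimate, which equals the assumed shift less whatever part of it persists.
4. **The benefit is partial.** The primary outcome is probably unaffected, and self-report at follow-up stays open to expectancy in an unmasked wait-list design whatever is done at V1. Both points stand. They limit what the change achieves, but they are no reason to keep an avoidable baseline component.

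**Conclusion.** The concern holds. Followed as written, V1 lets participants know their group before the secondary baselines are taken, and the analysis of change carries any resulting shift into the treatment contrast, less whatever part of it persists at follow-up. For a transient shift of 0.25 SD the estimate is wrong by 0.25 SD. The false-positive rate is then 8.3% to 10.5% under equal SDs and r of 0.5 to 0.7, or about 7.5% to 13.2% with the pilot SDs. At 0.1 SD, under the same equal-SD assumptions, the rate is close to nominal, and a fully persistent shift cancels. All shift sizes are assumptions.

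The finding concerns the secondary outcomes. The primary seated BP is probably protected, though no section says outright that the qualifying reading is the V1 baseline. This should be fixed because the risk is plausible, bears on the effect-size purpose of the pilot, and is nearly free to remove.

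**What to change.** - **Enrollment Visit:** replace the clause on notification and baseline measures with wording such as *the complete V1 battery, brainwave assessment included, is finished first; randomization and disclosure of the group follow*.
- **Participants/Subjects:** list medical history, then baseline measures, then randomization.
- **Both sections:** give one explicit V1 order: consent, qualifying BP, pregnancy test where applicable, medical history, all baseline measures, randomization, notification. The existing pregnancy-test and medical-history sentences are compatible with this, but stating the order once removes doubt.
- **Blood Pressure (BP):** add that the seated reading that qualifies the participant before randomization (the repeat, if one is taken) is the V1 baseline for the primary outcome.

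The cost is re-wording. Both arms already have the same V1 measures, including the brainwave assessment, in one visit of about 2 hours. Sessions start 0 to 14 days later, so no V1 measure needs the assignment. Sample size, procedures and visits do not change.
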